#### 4. TRIAL POPULATION

##### 4.1 NUMBER OF PARTICIPANTS

A total of 24 patients will be included in Edinburgh. Patients will be randomised to conventional treatment (8 patients) or to one of the following four surface cooling strategies (4 patients each): (A) 35°C maintained for 12 hours; (B) 33°C maintained for 12 hours; (C) 35°C maintained for 24 hours or (D) 33°C maintained for 24 hours.

##### 4.2 INCLUSION CRITERIA

Patients may be enrolled in the trial if all of the following criteria have been met:

1. A clinical diagnosis of acute ischaemic stroke in accordance with WHO criteria;
2. Arrival at the hospital within 3 hours of symptom onset and a possibility to initiate cooling within 90 minutes of hospital admission. Onset time for patients who awoke with symptoms is defined as the last time the patient was awake without symptoms of stroke;
3. Score on the National Institutes of Health Stroke Scale (NIHSS)  $\geq 4$ ;
4. Age  $\geq 18$  years;

##### 4.3 EXCLUSION CRITERIA

Patients will be excluded from the trial for any of the following reasons:

1. Evidence from a CT or MRI scan or from other pre-randomisation investigations of an intracranial haemorrhage, a tumour, encephalitis, or any diagnosis other than acute ischaemic stroke likely to be the cause of present symptoms. (Mild haemorrhagic transformation of the infarct, defined as petechial haemorrhage, is not an exclusion criterion);
2. Conditions that may be exacerbated by hypothermia, such as haematological dyscrasias, oral anticoagulant treatment with INR  $>1.5$ , severe pulmonary disease, severe heart failure (defined as a New York Heart Association (NYHA) score of III or IV), history of myocardial infarction within the previous three months, angina pectoris in the previous three months, severe infection with a leukocyte count  $>15/\text{ml}$  and a CRP  $>50\text{mg/dl}$ , or a clinical diagnosis of sepsis;
3. Contraindication to MR scanning;
4. Oxygen saturation below 92% without use of oxygen therapy or below 94% with a maximum of 2 L/min oxygen delivered nasally;
5. Bradycardia ( $<40$  beats/min);
6. Body weight  $> 120$  kg;
7. Pre-stroke score on the modified Rankin Scale (mRS)  $> 2$ ;
8. Allergy to pethidine, use of a monoamine oxidase inhibitor such as selegiline in the previous 14 days, severe hepatic dysfunction, or severe renal dysfunction;
9. Pregnancy. Women of childbearing potential are excluded unless a negative test for pregnancy has been obtained prior to randomisation;
10. Other serious illness that may confound treatment assessment or increase the risks of cooling;
11. Previous participation in this trial;
12. Social or other conditions that according to the investigators judgement might be a major problem for follow-up.

Note: Treatment with intravenous rt-PA is not an exclusion criterion.

## **5. PARTICIPANT SELECTION AND ENROLMENT**

### **5.1 IDENTIFYING PARTICIPANTS**

Potential patients will be screened by the receiving stroke team on referral.

### **5.2 CONSENTING PARTICIPANTS**

Informed consent for this trial will be obtained from the patient prior to the performance of any protocol-specific procedure. Assessments or tests described in the protocol which would have been performed as part of the patient's routine clinical evaluation (i.e. not specifically performed for this trial) do not require consent. The patient may withdraw consent at any time.

If potential patients are unable to provide written informed consent or witnessed verbal consent, the patient's relative or welfare guardian can agree to their participation. In this case a consent form needs to be completed. The relative or welfare guardian can withdraw their consent at any time.

If a patient with mental incapacity has been enrolled but then regains mental capacity the team should ensure that the patient is informed about the trial and should confirm that the patient is willing to continue to participate. Where practical the patient should be given the appropriate patient information brochure and sign a consent form.

### **5.3 SCREENING FOR ELIGIBILITY**

Acute stroke referrals in Lothian are triaged through an on call consultant to determine eligibility for thrombolytic treatment with intravenous tPA. The eligibility of these patients for the current trial will be assessed at that time.

### **5.4 INELIGIBLE AND NON-RECRUITED PARTICIPANTS**

A screening log will collect data on ineligible and non-recruited patients at each centre, with reasons for non-recruitment where these are known.

### **5.5 RUN IN PERIOD**

The protocol requires that randomised patients be transferred for MR scanning three hours after the initiation of cooling. While we expect that this will be feasible, we will first cool 3 non-randomised patients to 35°C in the High Dependency Unit setting so that we may focus on streamlining that part of the trial. These patients will be given a separate patient information leaflet and informed consent form, and these are shown in Appendix 5.

### **5.6 RANDOMISATION**

#### **5.6.1 Randomisation**

After written informed consent has been obtained, patients will be randomised to conventional treatment or to one of the following four surface cooling strategies: (A) 35°C maintained for 12 hours; (B) 33°C maintained for 12 hours; (C) 35°C maintained for 24 hours or (D) 33°C maintained for 24 hours, using a length-of-time escalation design (see next paragraph). Randomisation will be stratified for the intention to perform intravenous thrombolysis with rt-PA and for stroke severity (dichotomised between NIHSS scores of 13 and 14). The choice to perform intravenous thrombolysis is left at the discretion of the local investigator. Allocation to treatment will be through a web-based randomisation service hosted at the University of Edinburgh. Each active treatment arm will consist of 4 patients and the control group of 8 patients.

#### **5.6.2 Treatment Allocation**

All patients will be managed in the High Dependency Unit at the Western General Hospital. Because of the potential discomfort of prolonged cooling to low temperatures, and the learning required efficiently to deliver cooling to awake patients, we will randomise in blocks of 12, each block including 4 patients allocated to standard care. The first 12 patients will be randomised 1:1:1 to 35°C for 12 hours; 33°C for 12 hours; or standard care (Groups A and B). Patients 13-24 will be randomised 1:1:1 to 35°C for 24 hours; 33°C for 24 hours; or standard care (Groups C and D).

In all patients randomised to hypothermia, cooling will be started within 4.5 hours after the onset of symptoms and within 90 minutes of hospital admission by means of intravenous infusion of 25ml/kg refrigerated normal saline (4°C) over 30 minutes.

In patients randomised to hypothermia, surface cooling will be applied to the thighs and chest immediately after the start of the saline infusion using five Arctic Sun Energy Transfer Pads, connected to an Arctic Sun temperature control module with integrated chiller (Medivance, Inc). Inlet water temperature will be automatically controlled to achieve a target oesophageal temperature of 35°C or 33°C.

Start of treatment will be defined as the start of cooling, i.e. start of infusion of refrigerated saline. Active cooling will be continued for 12 or 24 hours. Thereafter, patients will be passively warmed at a rate controlled by the cooling device to be at most 0.3°C per hour until the oesophageal temperature is 36°C; the cooling device will then be disconnected.

Oesophageal temperature will be measured with probes providing feedback to the Arctic Sun. In addition to the continuous oesophageal recordings, tympanic temperature will be recorded before cooling is started and subsequently at 15-minute intervals with a standard tympanic thermometer. Where other temperature measurements are made as part of standard care, these data will also be recorded. Level of consciousness, presence or absence of shivering, blood pressure and heart rate will be recorded every 15 min for the whole cooling and warming phase.

To prevent shivering and discomfort in patients randomised to hypothermia, a protocol similar to that used in ICTuS-L will be applied. However, pethidine starting doses will be lower because of higher target temperatures in the current trial than in ICTuS-L. Patients randomised to hypothermia will receive a loading dose of pethidine 0.5 mg/kg intravenously over 5 minutes, followed by a pethidine dose of 0.25 mg/kg/h intravenously, which may be adjusted over time on the basis of a published four point shivering scale. If shivering does occur, the patient will be given a bolus of 10 to 25 mg pethidine intravenously, followed by an increase in the continuous infusion of 5 mg/h. If at any time significant sedation begins to develop, the pethidine maintenance dose will be lowered. To mitigate any possible narcotic-related emesis, the patient is fasted, and a nasogastric tube is inserted and attached to continuous low wall-suction. In addition, patients randomised to hypothermia will wear gloves and socks to reduce the sensation of cold.

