## SUMMARY

**Background:** Animal studies strongly suggest that cooling improves outcome after ischaemic stroke. Cooling is probably most efficacious with temperatures of 34°C or below, but such temperatures may not be tolerated well by awake patients on a stroke unit. Cooling to 35°C may have a smaller but still substantial effect on outcome and may be achievable for large numbers of patients with ischaemic stroke. Large randomised clinical trials testing whether cooling improves outcome in patients with acute ischaemic stroke are warranted, but the optimal strategies to achieve hypothermia are uncertain. The aim of this pilot phase is to compare the feasibility and safety of surface cooling to 35°C, started within 4.5 hours after the onset of acute ischaemic stroke and maintained for 12 hours, with strategies aimed at reaching a temperature of 33°C and/or maintaining hypothermia for 24 hours.

**Methods:** This is a pilot phase for a randomised, open, multi-centre, phase III international clinical trial with masked outcome assessment, comparing four different surface cooling strategies with standard treatment in awake adult patients with acute ischaemic stroke. A total of 24 patients will be randomised in the Edinburgh pilot, with a further 2-3 pilots planned elsewhere in Europe. Patients will be randomised to conventional treatment (8 patients) or to one of the following four surface cooling strategies (4 patients each): (A) 35°C maintained for 12 hours; (B) 33°C maintained for 12 hours; (C) 35°C maintained for 24 hours or (D) 33°C maintained for 24 hours. Before randomisation begins we will recruit 3 patients to be cooled to 35°C maintained for 12 hours (but without the biomarker component) to streamline the patient pathway. In the randomised pilot phase we will use a dose escalation approach to ensure that the longer cooling duration is only performed once we have gained sufficient experience with shorter duration cooling.

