### 1.2.3 Depth of Hypothermia

COOL AID, as well as most randomised trials of hypothermia in postanoxic encephalopathy after cardiac arrest, perinatal hypoxic-ischemic encephalopathy, and traumatic brain injury have tested cooling to levels of 32°C to 34°C. For patient comfort, monitoring, and the prevention of shivering, hypothermia to these levels generally requires sedation, mechanical ventilation, and therefore admission to an intensive care unit. Due to the limited availability of intensive care beds in most countries, treatment of even a minority of acute stroke patients is therefore precluded by substantial practical and logistical problems. The fact that intensive care treatment has long been common clinical practice for patients with severe traumatic brain injury or after cardiac arrest may explain why large and definitive randomised clinical trials of moderate hypothermia have been accomplished in these patient populations, whereas such trials have not even been started in patients with acute ischaemic stroke.

In a recent systematic review and meta-analysis of hypothermia in animal models of acute ischaemic stroke, hypothermia reduced infarct size by more than 40% with temperatures of 34°C or below. However, infarct size was still reduced by 30% (95% confidence interval (CI), 21 to 39%) with cooling to 35°C, suggesting that even very modest cooling has considerable potential as a neuroprotective strategy. Temperature reductions to 35.5°C or 35°C have been shown feasible and safe in awake patients with acute ischaemic stroke by surface cooling, in combination with pethidine (meperidine) to treat shivering. With a similar strategy, body temperature could be reduced to 34.5°C in awake patients with acute myocardial infarction.

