#### 2.2.2 Secondary Endpoints

- Feasibility (recruitment rate; time to target temperature; stability at target; control of temperature during warming period)
- Tolerability (Columbia Shivering Score; patient questionnaire)
- Safety (deaths; adverse events including infections, DVT or coagulopathy; pethidine dose required)
- Oesophageal temperatures compared with tympanic, and bladder and/or rectal where available, at baseline, every 15 minutes in the first three hours after start of cooling and every 30 minutes thereafter until 48 hours after stroke onset
- Penumbra temperature 3 hours after initiation of cooling
- National Institutes of Health Stroke Scale (NIHSS) score, the Barthel Index (BI) and the modified Rankin scale (mRS) at three months
- Infarct volume on CT or MRI 7 days after the induction of hypothermia
- Temperature in ischaemic core, surrounding brain, and contralateral hemisphere determined using MR spectroscopy initiated 2-3 hours after the commencement of cooling
- Feasibility of collecting and processing samples for future biomarker study.

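### The 24-hour cooling arms open on a head count at patient 13, with no review of block-1 tolerability and safety tied to the step

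*Protocol*

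**What the plan says.** The Summary describes a dose escalation approach whose purpose is "to ensure that the longer cooling duration is only performed once we have gained sufficient experience with shorter duration cooling". Section 5.6.1 labels the design an escalation by duration and refers the reader on to 5.6.2.

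Section 5.6.2 gives two reasons for randomising in blocks of 12: the discomfort that long cooling to low temperatures may cause, and the learning that staff need. It then gives the operating rule. The first 12 patients go to 35°C for 12 hours, 33°C for 12 hours or control. After that, "Patients 13-24 will be randomised 1:1:1 to 35°C for 24 hours; 33°C for 24 hours; or standard care". Nothing else in 5.6.2 governs the move.

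Before block 1 there is a run-in: "Before randomisation begins we will recruit 3 patients to be cooled to 35°C maintained for 12 hours". Section 5.5 says its aim is to streamline the transfer to MR scanning.

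On depth, the protocol treats the two targets differently. For 35°C it says "Temperature reductions to 35.5°C or 35°C have been shown feasible and safe in awake patients with acute ischaemic stroke by surface cooling". For 32°C to 34°C it says that "hypothermia to these levels generally requires sedation, mechanical ventilation, and therefore admission to an intensive care unit", and the Summary warns, of 34°C or below, that "such temperatures may not be tolerated well by awake patients on a stroke unit".

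**The concern.** An escalation step protects patients if someone looks at the lower step before the higher one opens. Here the count advances with each patient randomised, so a cooling abandoned for distress moves the trial towards 24 hours as much as one that was tolerated well. A count can show that staff have had practice. It cannot show whether patients tolerated the treatment, and discomfort is one of the protocol's own two reasons for the blocks.

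At stake are the 8 patients allocated to 24-hour cooling, above all the 4 at 33°C. That is the target for which the protocol itself expresses most doubt in awake patients, and its duration would double without a planned look at how the shorter duration went.

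**Working it through.** **1. Structure of the plan.** Two blocks of 12 at 1:1:1 give 4 patients per arm in each block. Cooled: 2 × 8 = 16. Control: 2 × 4 = 8. Total: 24. This reproduces the figures in 4.1 and 5.6.1.

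**2. Planned cooling experience when patient 13 is randomised** (Summary, 5.5, 5.6.2).

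| | 35°C | 33°C | Total |
|---|---|---|---|
| Run-in, 12 h | 3 | 0 | 3 |
| Block 1, 12 h | 4 | 4 | 8 |
| Before patient 13 | 7 | 4 | 11 |
| Opened at patient 13, 24 h | 4 | 4 | 8 |

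Within this trial, the longer duration at 33°C rests on 4 planned patients.

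**3. Is a review tied to the step anywhere else?**

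- 5.6.2 and 6.0.3: recording every 15 minutes during cooling, and NIHSS at 24 and 48 hours. These concern the individual patient.
- 8.2 and 8.4: the investigator reviews each event, and SAEs are reported within 24 hours. These work event by event.
- Section 6: safety and other data from all the pilots are collated in Edinburgh with a statistician. This is aggregate, but no timing, look by arm or decision is stated.
- 10.4 and 10.5: the steering committee oversees conduct and the DMC oversees safety across all pilots. Neither section mentions block 1 or patient 13.
- 12.4: the investigators and/or the steering committee may terminate at any time. No criteria are given and the step is not mentioned.
- 7.2: concerns about 33°C or 24 hours would change the regimen, but the regimen meant is the one for phase III.

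None of these makes the opening of the 24-hour arms depend on block-1 results.

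**4. Would poor tolerability surface as an SAE?** Section 8.1 requires death, threat to life, hospitalisation or its prolongation, lasting disability, or a birth defect. Heavy shivering, high pethidine need, sedation short of these, or stopping because of distress can all occur without meeting that definition. Pethidine dose and shivering score are already endpoints in 2.2.2, so the data for a review would exist.

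**5. What a review could detect.** For 0 affected of n, the exact 95% upper limit is 1 − 0.025^(1/n).

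- n = 4 (one temperature): 1 − 0.398 = 60.2%
- n = 8 (both temperatures): 1 − 0.631 = 36.9%

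With an assumed true rate p of serious intolerance at 33°C (the protocol gives none), P(at least 2 of 4) = 1 − (1−p)^4 − 4p(1−p)^3.

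- p = 0.2: 1 − 0.4096 − 0.4096 = 0.18
- p = 0.5: 1 − 0.0625 − 0.25 = 0.69

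At p = 0.8, P(at least 3 of 4) = 4(0.8³)(0.2) + 0.8⁴ = 0.82. The review would usually show a gross problem and would often miss a moderate one.

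**The case against.** The strongest reply is that this is mainly a learning step. The Summary asks for experience, not for satisfactory results, and 3 run-in plus 8 block-1 coolings supply experience by count. That stands in part. A reader might infer that 5.6.2 contradicts the Summary, and it does not. But the discomfort reason in 5.6.2 is not met by a count.

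A reader might also infer that the 24-hour arms would open whatever happened in block 1. The documents support that only for the allocation sentence. An independent DMC, rapid SAE reporting, central collation and a power to terminate could all stop the trial. Treatment is open and given in one High Dependency Unit, where trouble in 4 patients would be hard to miss. This stands, and it limits the point to the absence of a link between those safeguards and the step.

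A third tempting reading is that 4 non-completions out of 4 at 33°C for 12 hours ought to have closed the 33°C, 24-hour arm. Completion is the primary endpoint, and it can fail for logistical or device reasons that say nothing about safety, so a bare completion count is not a stopping signal.

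There is also outside evidence at 33°C. Section 1.2.2 cites a randomised stroke trial of 40 patients with a target of 33°C for 24 hours, and 8.0.1 cites cardiac arrest trials at 32°C to 34°C without an excess of adverse effects. The first used intravascular cooling and the others treated a different population, so they reduce the concern about surface cooling in awake stroke patients without removing it.

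Finally, a DMC charter may schedule looks. None is shown, the protocol does not refer to one, and the rule in 5.6.2 does not depend on one.

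**Conclusion.** The point holds in a limited form. The protocol states a protective purpose for the escalation and gives discomfort as a reason for it, but the only operating rule is a patient number. General oversight could stop the trial after a disaster. It does not ensure that anyone looks at block-1 tolerability and safety by arm before 8 patients are allocated 24-hour cooling, 4 of them at 33°C after only 4 planned coolings at that temperature.

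This is a matter of trial conduct and patient safety. It changes no sample size, error rate or analysis. The counts follow directly from the protocol. The detection probabilities rest on assumed rates of intolerance and show only that a look at 4 patients per temperature is coarse. The conclusion also assumes that no unseen charter already ties a DMC look to patient 13.

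**What to change.** State in 5.6.2 and 10.5 that patient 13 is not randomised until:

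1. all block-1 coolings and rewarmings are finished; and
2. the existing DMC has reviewed block-1 data by arm (completion with reasons for stopping, shivering score, pethidine dose, adverse events, NIHSS to 48 hours) and has confirmed that each 24-hour arm may open.

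Add that stopping for safety or intolerance counts in that judgement, while stopping for logistical or device reasons does not by itself close an arm. The DMC is the right body, because under 6.0.4 steering committee members score the mRS and Barthel Index blind to allocation.

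**Cost.** A few sentences of text and one review of 12 patients; planned N and arm sizes do not change. The longest block-1 treatment takes at least 12 + (36 − 33)/0.3 = 22 hours, so the 48-hour NIHSS of patient 12 will normally set the wait: 2 days plus DMC turnaround, which the protocol does not state. If turnaround is assumed to be 7 to 14 days, the pause is 9 to 16 days. At an assumed one eligible patient every 30 days to every 7 days, that misses 9/30 = 0.3 to 16/7 = 2.3 patients, which is a delay and not a loss of N. If the DMC withholds an arm, its 4 patients and that part of the four-strategy comparison are lost.

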In all patients randomised to hypothermia, cooling will be started within 4.5 hours of the onset of symptoms by means of intravenous infusion of 20 ml/kg cooled normal saline (4°C) over 30 minutes, followed by surface cooling using the Arctic Sun device. Shivering and discomfort will be prevented and if necessary treated with intravenous pethidine. The primary objective is to determine the feasibility, tolerability and safety of the various cooling strategies, as evidenced by the primary endpoint, the proportion of completed interventions. Secondary outcome measures include measures of the safety and tolerability of the intervention.

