### 1.2.2 Previous and Ongoing Studies

So far, clinical trials of cooling in patients with acute ischemic stroke have been too few and too small to allow any conclusions. The Cooling for Acute Ischemic Brain Damage (COOL AID) trial is the only published randomised controlled trial and included just 40 patients where cooling to a target temperature of 33°C for 24 hours was initiated within 12 hours of stroke onset using intravascular cooling. The Nordic Cooling Stroke Trial (NOCSS) was a randomised trial which tested the effect of surface cooling to 35°C initiated within 6 hours of stroke. Unfortunately, the trial was recently terminated because of slow recruitment after the inclusion of 44 patients against a target recruitment of 1,000 ([name], personal communication). The ongoing Intravascular Cooling for the Treatment of Stroke – Longer window (ICTuS-L) trial is a phase II trial designed to investigate the feasibility and safety of a combination of intravenous thrombolysis and intravascular cooling to 33°C. The only large temperature-driven phase III randomised acute stroke trial is the Paracetamol (Acetaminophen) In Stroke (PAIS) trial, which sought normalisation of temperature rather than hypothermia; overall, this showed no benefit, although in a post hoc analysis there was a suggestion that patients with pyrexia at entry may have benefited.

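### The cold saline volume is 20 ml/kg in the Summary and 25 ml/kg in section 5.6.2 for the same patients; the pethidine rationale and the infection cut-off units also need correcting

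*Protocol*

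**What the plan says.** **Saline.** For patients allocated to cooling, the Protocol Summary describes "intravenous infusion of 20 ml/kg cooled normal saline (4°C) over 30 minutes", followed by surface cooling. Section 5.6.2 describes the same step: "In all patients randomised to hypothermia, cooling will be started within 4.5 hours after the onset of symptoms", by means of "25ml/kg refrigerated normal saline (4°C) over 30 minutes". Section 5.6.2 also defines the start of treatment as the start of this infusion.

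**Pethidine.** Section 5.6.2 follows an anti-shivering scheme like that of ICTuS-L, with one change: "pethidine starting doses will be lower because of higher target temperatures in the current trial than in ICTuS-L". It then gives a single regimen for all cooled patients: a loading dose, a maintenance infusion, and adjustment on a shivering scale. Section 1.2.2 describes ICTuS-L as testing "a combination of intravenous thrombolysis and intravascular cooling to 33°C". Arms A and C of the present trial target 35°C; arms B and D target 33°C.

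**Infection exclusion.** Section 4.3, item 2, excludes "severe infection with a leukocyte count" above 15/ml together with a CRP above 50 mg/dl. A clinical diagnosis of sepsis is a separate alternative.

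**The concern.** The saline infusion is part of the intervention, and two sections of current text prescribe different amounts for the same patients, at the same temperature and over the same time. Staff following the Summary and staff following section 5.6.2 would give different treatments, and both could say they had followed the protocol. The volume bears on how fast patients cool, and time to target temperature is a listed feasibility outcome (sections 2.2.2 and 3). It also bears on safety, since a large volume goes in within half an hour. Section 3 plans to align protocols with other European pilots for a pre-planned meta-analysis, which needs one stated volume.

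The other two items are smaller. The pethidine sentence gives a reason that the protocol's own description of the comparison trial contradicts for half of the cooled patients. The infection criterion carries a leukocyte unit that does not work as a cut-off and a CRP value that is extreme as printed. It sits in the list of conditions that hypothermia may worsen, and infection is a listed safety outcome in section 3.

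**Working it through.** No power or sample-size formula applies here. The check compares sections and does simple arithmetic.

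**Patient count.** Section 5.6.1 gives 4 patients per cooling arm and 8 controls: 4 × 4 + 8 = 24, which reproduces the total in section 4.1. Cooled patients: 4 × 4 = 16. Patients in the 33°C arms B and D: 2 × 4 = 8.

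**Saline.** Inputs: 20 ml/kg (Summary), 25 ml/kg (section 5.6.2), 30 minutes in both, weight limit 120 kg (section 4.3, item 6). The 70 kg weight is an assumption for illustration.

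- Relative difference: 25 / 20 − 1 = 25%.
- At 70 kg: 20 × 70 = 1,400 ml against 25 × 70 = 1,750 ml, a gap of 350 ml. As a rate over half an hour: 2.8 against 3.5 litres per hour.
- At 120 kg: 20 × 120 = 2,400 ml against 25 × 120 = 3,000 ml, a gap of 600 ml.

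Patients, fluid temperature and duration match in the two sections. Only the volume differs.

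**Pethidine rationale.** Target in this trial minus the ICTuS-L target of 33°C in section 1.2.2:

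- Arms A and C: 35 − 33 = +2°C. The stated reason holds.
- Arms B and D: 33 − 33 = 0°C. The stated reason fails.

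Share of cooled patients for whom it fails: 8 / 16 = 50%. The ICTuS-L dose is not in the protocol, so the size of the reduction cannot be worked out.

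**Infection cut-offs.**

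- Leukocytes: 15 per ml × 1,000 = 15,000 per litre = 0.000015 × 10⁹/L. Assume an ordinary range of 4 to 11 × 10⁹/L, that is 4 to 11 million per ml. Then 4,000,000 / 15 ≈ 270,000 and 11,000,000 / 15 ≈ 730,000, so ordinary counts exceed the printed cut-off by those factors.
- CRP: 50 mg/dl × 10 = 500 mg/L.
- The two limbs are joined so that both must be met. If every patient meets the leukocyte limb, the criterion reduces to severe infection with CRP above 50 mg/dl, or clinical sepsis.

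**The case against.** **On the saline,** one can say that a summary is only an abstract and that the detailed section governs. That is a common convention, but the protocol states no such precedence. It is also fair that either volume, used throughout, would apply to all four cooling arms. It would then not by itself distort 33°C against 35°C, or 12 against 24 hours. The device controls to the oesophageal target afterwards, so the main documented effect is on induction speed. The safety outcomes listed in section 3 name no fluid-overload event, so that consequence is a clinical inference and not something the protocol sets out to measure by name. These points limit the consequence; the contradiction remains.

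**On pethidine,** a reader might infer that treatment is left unfixed, or that the 33°C arms could look intolerable because they were under-dosed. The protocol does not support either reading. The regimen appears once, covers all cooled patients, and is contradicted nowhere. It is a starting dose with a bolus and an infusion increase if shivering occurs. Shivering is scored every 15 minutes and the pethidine dose required is a secondary endpoint, so a greater need at 33°C would be treated and recorded. What stands is that the written reason is wrong for arms B and D.

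**On the infection criterion,** a reader might infer that both units are impossible and that the exclusion catches almost nobody. That goes too far. A CRP in mg/dl is a valid unit, and 500 mg/L is extreme but possible. Clinical sepsis remains an exclusion in the same item, and item 10 covers other serious illness that may raise the risks of cooling. The leukocyte point rests on an ordinary laboratory range, not on a conflict between sections, and a multiplier lost when the PDF was read cannot be ruled out. A request to check the units is justified.

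**On pooling,** a reader might infer that the other centres cannot align their protocols. Nothing in the document shows that; it shows only that one volume has to be settled and shared.

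**Conclusion.** The saline contradiction stands and must be corrected. Two volumes that differ by 25% are prescribed for all 16 cooled patients, in a step that defines the start of treatment and bears on a listed outcome. The litre figures rest on an assumed 70 kg and on the protocol's own 120 kg limit; the 25% rests on nothing beyond the two printed figures.

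The pethidine rationale is inaccurate for 8 of the 16 cooled patients. That is an error of explanation: the dose is given once and titrated.

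The leukocyte cut-off as printed does not discriminate, given an assumed range of 4 to 11 × 10⁹/L. The CRP cut-off as printed equals 500 mg/L. This part carries less certainty, because the printed units have first to be confirmed against the original document.

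The sample size and the planned analyses are unaffected.

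**What to change.** 1. Reconcile the Summary and section 5.6.2 to one saline volume before the first patient is treated, and send that volume to the other pilot centres whose protocols are to be aligned.
2. Have the clinical leads reconcile the pethidine rationale in section 5.6.2 with the ICTuS-L target in section 1.2.2 and with the 33°C target of arms B and D.
3. Check both units in section 4.3, item 2, against the original document and the laboratory's reporting units, and correct whatever proves to be misprinted.

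The choice of volume, dose and thresholds belongs to the clinical leads; this review proposes none. The cost is a protocol text correction, with no extra patients and no change to the analysis.
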